#### **14.4 Echocardiograms (ECGs)**

Values of heart rate, PR, QRS, QT and QTcF, the interpretation and the clinical significance of the ECG will be summarized by individual Cohorts (i.e., Cohorts: A, A1, A2, A3, A4, A5, A6, B, B1, B2) using descriptive statistics for 12-Lead ECG/ Lead II Rhythm Strip. In addition, QTcF will be summarized using categories as defined in ICH E14 (i.e., QTcF (ms): >450-480; >480-500; >=500).

The Bazett's Correction (QTcB) and Fridericia's Correction (QTcF) are derived as follows:

$$\text{Bazett's Correction (QTcB)} \quad QTc_b = \frac{QT}{\sqrt{RR}}$$

QMS Document Name: Statistical Analysis Plan	Page 23 of 29
QMS No (include version ref): STF-015-GL.02	Document date: 09JUL2019
CONFIDENTIAL	

$$\text{Fridericia's Correction (QTcF)} \quad QTc_f = \frac{QT}{\sqrt[3]{RR}}$$

where: RR = RR-interval measured in seconds.

ECG results will be listed including clinically significant data for the 12-lead ECG.

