## **7 Endpoints**

### **7.1 Safety Endpoints**

The endpoints to assess the safety of ALM-488 include:

- Adverse Events (TEAEs)
- Vital signs
- Clinical laboratory evaluations
- ECGs
- Physical examinations

Summaries of AEs will be based on Treatment Emergent Adverse Events (TEAEs) and will be summarized separately for each device and each of the Cohorts A1-A6, B1 and B2, as well as overall for Cohort A and Cohort B.

Vital signs, labs, ECGs, and physical exams will be summarized separately for each of the Cohorts A1-A6, B1 and B2, as well as overall for Cohort A and Cohort B.

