### **8.6 Baseline Definition**

For all variables, baseline will be considered to be the last value obtained prior to the date and time of incision. Change from baseline will be the difference between the value at a given time point and the baseline value. The baseline value corresponds to the screening visit in the study schedule.

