#### **14.2 Vital Signs**

The actual values and the change from baseline in vital signs will be summarized over time with n, mean, standard deviation, and median, minimum, and maximum.

Vital signs i.e. height, weight, systolic blood pressure, diastolic blood pressure, heart rate, and respiratory rate will be summarized descriptively over time by individual Cohorts (i.e., Cohorts: A, A1, A2, A3, A4, A5, A6, B, B1, B2).

Furthermore, the number and percentage of subjects based on reference ranges will be described according to the derived categories (i.e. Low, Normal, High) for vital signs.

A listing of vital signs will be presented for all measurements

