#### **14.3 Clinical Laboratory evaluations**

##### **Hematology, Clinical Chemistry, and Coagulation, Urinalysis**

All laboratory data will be listed by individual cohort, patient and time point and if normal ranges are available abnormalities will be flagged. Summary statistics will be provided by study dose and time point.

The Hematology parameters include: red blood cells, hemoglobin, hematocrit, mean corpuscular volume, mean corpuscular hemoglobin, mean corpuscular hemoglobin concentration, white blood cells, neutrophils, eosinophils, basophils, lymphocytes, monocytes, %neutrophils, %eosinophils, %basophils, %lymphocytes, %monocytes.

The clinical chemistry parameters include: alkaline phosphatase, AST/SGOT, ALT/SGPT, total bilirubin, calcium, phosphorus, blood urea nitrogen, creatinine, GFR, total protein, albumin, glucose, potassium, sodium, chloride, magnesium, bicarbonate, uric acid, lactate dehydrogenase.

Coagulation parameters include: PT, aPTT, INR.

The urinalysis analysis will include protein, blood, leukocytes, glucose, ketones and pH.

QMS Document Name: Statistical Analysis Plan	Page 22 of 29
QMS No (include version ref): STF-015-GL.02	Document date: 09JUL2019
CONFIDENTIAL	

Quantitative data will be examined for trends using descriptive statistics (number of patients with data, number of patients with missing values, mean, standard deviation, median, minimum, and maximum) of actual values and changes from baseline to each visit/time point. This will be presented by individual Cohorts (i.e., Cohorts: A, A1, A2, A3, A4, A5, A6, B, B1, B2).

Quantitative data based on reference ranges will be described according to the NCI-CTCAE version 5.0 grade at each visit over time and by individual Cohorts (i.e., Cohorts: A, A1, A2, A3, A4, A5, A6, B, B1, B2).

Qualitative data will be described according to the categories (i.e. Normal; Abnormal, Not clinically significant; Abnormal, Clinically significant; Missing) and by individual Cohorts (i.e., Cohorts: A, A1, A2, A3, A4, A5, A6, B, B1, B2).

Shift tables of quantitative data showing changes with respect to the normal range and clinical significance between baseline and endpoint post-baseline visits as well as the worst value at any post-baseline visit.

Shift tables of qualitative data showing changes between baseline and post-baseline visits.

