**ELECTROCARDIOGRAMS**  
 Table 14.3.5.1 12-Lead Electrocardiography/ Lead II Rhythm Strip, Cohort A Analysis Set: SAF  
 Table 14.3.5.2 12-Lead Electrocardiography/ Lead II Rhythm Strip, Cohort B Analysis Set: SAF

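### The ECG section specifies no change from baseline and no pre- and post-infusion time points, and sorts QTcF only by absolute value, so an individual QTcF rise after infusion is left to the listings

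*SAP*

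**What the plan says.** SAP section 7.1 lists ECGs among the safety endpoints and states that "Vital signs, labs, ECGs, and physical exams will be summarized separately for each of the Cohorts A1-A6, B1 and B2", with overall summaries for Cohorts A and B. Section 14.4 covers heart rate, PR, QRS, QT and QTcF with descriptive statistics, and says that "the interpretation and the clinical significance of the ECG will be summarized by individual Cohorts". For QTcF it adds that "QTcF will be summarized using categories as defined in ICH E14 (i.e., QTcF (ms): >450-480; >480-500; >=500". It also states that "ECG results will be listed including clinically significant data for the 12-lead ECG". It mentions no visit, time point, change from baseline or shift.

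The neighbouring sections are more specific. For vital signs (14.2), "The actual values and the change from baseline in vital signs will be summarized over time". For laboratory data (14.3), descriptive statistics are given "of actual values and changes from baseline to each visit/time point", with shift tables that include the worst post-baseline value. Physical examinations (14.5) are summarised at five named time points with change from baseline.

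Section 8.6 gives a general definition: "Change from baseline will be the difference between the value at a given time point and the baseline value". It sets baseline, for every variable, at the last value before incision, and also says that this corresponds to the screening visit. Sections 14.3 and 14.5 instead attach the word baseline to the assessment before ALM-488 infusion, and list it separately from screening.

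**The concern.** Each dose level has 3 to 6 subjects (section 4.1) and there is no randomised control (section 4.2). A subject's own value before infusion is therefore the natural reference for judging an ECG reading afterwards. Section 14.4 does not use it. The only QTcF display that goes beyond general descriptive statistics sorts readings by absolute length. A subject who entered with a long QTcF is flagged whether or not anything changed, and a subject with a large rise from a short starting value is not flagged at all. At stake is whether the planned summary of a primary-objective safety measure can point the reader to a rise after infusion, or whether the reader must find it in the listings.

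**Working it through.** Section 14.4 states no sample size, power or effect size, so there is no plan figure to reproduce. The QTcF values below are hypothetical, and the 60 ms rise is an example, not a threshold from the documents.

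**1. The SAP sections side by side**

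| Measure | Time points named | Change from baseline | Category or shift display |
|---|---|---|---|
| Vital signs (14.2) | over time | yes | low, normal, high |
| Laboratory (14.3) | each visit or time point | yes | CTCAE grade; shift tables with worst post-baseline value |
| Physical examination (14.5) | five, including before and after infusion | yes | none |
| ECG (14.4) | none | no | absolute QTcF bands only |

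Section 8.6 defines change from baseline but does not order an ECG summary of it. Section 20.1 lists separate shift tables for laboratory data and none for ECGs.

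**2. The bands applied as printed**

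- 440 and 450 ms: no band.
- 450.5 and 480 ms: first band.
- 481 and 499 ms: second band.
- 500 ms: second and third bands.
- 501 ms: third band.

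The overlap affects only a reading of exactly 500 ms.

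**3. Absolute bands against within-subject change, for three subjects**

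| Subject | Before (ms) | After (ms) | Change (ms) | Band before | Band after |
|---|---|---|---|---|---|
| 1 | 455 | 455 | 0 | >450-480 | >450-480 |
| 2 | 385 | 445 | +60 | none | none |
| 3 | 390 | 450 | +60 | none | none |

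The band count is 1 of 3 before and 1 of 3 after. The one flagged subject did not change, and the two who rose are not flagged.

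If values are summarised by visit, the mean goes from (455 + 385 + 390)/3 = 410 ms to (455 + 445 + 450)/3 = 450 ms. A rise of 40 ms is then visible, but not that it consists of 0, 60 and 60 ms. A single subject rising 60 ms moves the visit mean by 60/3 = 20 ms in a cohort of 3, and by 60/6 = 10 ms in a cohort of 6.

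**4. The limiting case of no split by time**

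Take a cohort with 400, 410 and 420 ms before and 440, 450 and 460 ms after (+40 ms each), and another with the order reversed (−40 ms each). Pooled over time, both give mean 430.0 and SD 23.7 ms. This applies only if readings are pooled, which section 8.7 makes unlikely.

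**5. Which baseline**

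Cohort B is infused 3-5 hours (B1) or 1-3 hours (B2) before surgery (section 4.1). Under 8.6, an ECG taken after infusion but before incision would be the baseline. With 385 ms before infusion, 445 ms after infusion but before incision, and 445 ms after surgery, the change is 445 − 445 = 0 ms from the 8.6 baseline and 445 − 385 = 60 ms from the pre-infusion value. Whether an ECG is scheduled in that window cannot be checked, because the supplied protocol text ends with eligibility.

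**6. Precision after the fix**

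The 95% half-width for mean change is t(0.975, n − 1) × SD/√n. The documents give no SD, so 8 to 20 ms is assumed.

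- n = 3: 4.303 × 8/1.732 = 19.9 ms, and 4.303 × 20/1.732 = 49.7 ms.
- n = 6: 2.571 × 8/2.449 = 8.4 ms, and 2.571 × 20/2.449 = 21.0 ms.

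**The case against.** A reader might infer that ECGs will be pooled over all time points within a cohort, and that the study therefore cannot show a QT effect after infusion. The documents do not support that.

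- Section 8.7 says that data are analysed by the visit recorded in the database, and exempts no data type.
- Individual ECG results are listed (14.4; two listings numbered 16.2.14 in 20.2), and section 8.1 sorts listings by visit where appropriate. With 3 to 6 subjects per dose, individual changes should be readable there.
- Table layouts are in a separate document (section 2.1) that was not supplied. The title "Table 14.3.5.1 12-Lead Electrocardiography/ Lead II Rhythm Strip, Cohort A Analysis Set: SAF" mentions no time point or change, but neither do the titles of the main vital-signs and laboratory tables, whose text requires both. Its silence is not evidence.

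The objection stands against those stronger readings. It does not cure the gap. Section 8.7 divides Day 1 into pre- and post-operative, which does not separate before from after infusion, and it orders no ECG change summary. A listing is also not a summary; laboratory values and physical examinations are listed too, and still get change summaries.

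It is also fair that change is not the only safety information. Absolute outliers, clinical significance and graded adverse events are reported. Without a control group, change from baseline cannot by itself separate the drug from the surgery. The band overlap is trivial in practice, and outlier bands need not add up to the number of subjects. These points limit the weight of the concern without removing it.

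**Conclusion.** The concern holds for the planned summaries. Section 14.4 falls below the standard that the SAP sets for its other safety measures: it specifies no ECG change from baseline and no pre- and post-infusion time points, and its QTcF bands mix pre-existing length with any rise. Under a by-visit reading, a cohort mean shift would show, but an individual rise that stays at or below 450 ms would appear only in the listings. The overlap at 500 ms and the missing row for 450 ms or less are minor errors.

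This is a change that should be made; it does not invalidate the safety analysis. The conclusion rests on the SAP text alone. The unseen table specifications may already contain time points and changes. If so, section 14.4 should say so. The ECG schedule was not available, and whether the bands match ICH E14 was not assessed, nor does the conclusion depend on it.

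**What to change.** In section 14.4 and Tables 14.3.5.1 and 14.3.5.2:

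- Summarise ECG parameters by time point, with change from the last ECG before infusion.
- Add a table of QTcF category at that baseline against the worst category after infusion, and a row for the largest individual QTcF increase.
- Make the bands exclusive and complete, for example ≤450, >450-480, >480-500 and >500 ms.
- For ECGs, reconcile the pre-incision baseline in 8.6 (and its link to the screening visit) with the pre-infusion baseline in 14.3 and 14.5. Otherwise the new change column could be measured from an ECG taken after infusion.
- Where the ECG schedule allows, compute change within the same recording type (12-lead or Lead II rhythm strip).

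The cost is SAP wording and a somewhat larger descriptive table. If ECGs before and after infusion are already scheduled, which the supplied text does not show, no new data are needed. The summaries remain descriptive: with half-widths of about 20 to 50 ms at n = 3 and 8 to 21 ms at n = 6 under the assumed SDs, they describe individual subjects better than they estimate a mean effect.

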#### **14.5 Physical Examinations**

Results from physical examinations will be summarized by visit/timepoint (screening, prior to ALM-488 infusion (baseline), after ALM-488 infusion, Day 15, Day 28), change from baseline by individual Cohorts (i.e., Cohorts: A, A1, A2, A3, A4, A5, A6, B, B1, B2).

PE will be provided in a data listing by subject.

#### **14.6 Blood allergy**

Results from blood allergy parameters will be summarized by visit/timepoint (pre-infusion, end of infusion, thirty minutes after end of infusion and 22 hours after the end of infusion), by individual Cohorts (i.e., Cohorts: A, A1, A2, A3, A4, A5, A6, B, B1, B2).

Blood allergy will be provided in a data listing by subject.

#### **14.7 Pregnancy Tests**

All available data will be listed by individual Cohorts (i.e., Cohorts: A, A1, A2, A3, A4, A5, A6, B, B1, B2).

#### **14.8 Serum Samples**

All available data will be listed by individual Cohorts (i.e., Cohorts: A, A1, A2, A3, A4, A5, A6, B, B1, B2).

#### **14.9 Chest X-Ray/CT**

All available data will be listed by individual Cohorts (i.e., Cohorts: A, A1, A2, A3, A4, A5, A6, B, B1, B2).

### **15 Pharmacokinetic Analyses (PK)**

The PK analyses will be described in a separate PK SAP and will use the PP and PK analysis set.

### **16 Interim Analyses**

An interim analysis is not planned for this study.

### **17 Statistical Analyses for Safety Monitoring**

Whenever a cohort is completed or when needed based on safety and toxicity information, selected outputs from the final analysis will be created for safety monitoring by the IDMC. The content of these safety analyses is specified in a separate IDMC Charter.

QMS Document Name: Statistical Analysis Plan	Page 24 of 29
QMS No (include version ref): STF-015-GL.02	Document date: 09JUL2019
CONFIDENTIAL	

## 18 Statistical Analyses for Clinical Trial Registries

The following additional analyses will be performed for the purpose of fulfilling the Clinical Trial Registry (CTR) requirements:

Both Serious Adverse Events and Non-Serious Adverse Events will be summarized by MedDRA preferred term.

- An adverse event is considered 'Serious' whether or not it is a TEAE
- An adverse event is considered in the 'Non-Serious' category if it is both a TEAE and is not serious

For each Serious AE and Non-Serious AE, for each term and treatment group, the following are provided:

- the number of subjects at risk of an event;
- the number of subjects who experienced each event term;
- the number of events experienced.

## 19 Software

The data will be analysed using SAS Version 9.4 or higher.

QMS Document Name: Statistical Analysis Plan	Page 25 of 29
QMS No (include version ref): STF-015-GL.02	Document date: 09JUL2019
CONFIDENTIAL	

## 20 Tables, Listings, and Figures

### 20.1 Tables

Below is Table of Contents for the Tables.

#### SUBJECT DISPOSITION

- Table 14.1.1 Reasons for Screen Failure, cohort A Analysis set: ENR
- Table 14.1.2 Summary of Analysis Sets and Cohorts Analysis Set: ENR
- Table 14.1.3 Disposition and Discontinuation Reasons [1], Cohort A Analysis Set: ENR
- Table 14.1.3 Disposition and Discontinuation Reasons, Cohort B Analysis Set: ENR
- Table 14.1.4 Disposition by Site, Cohort A Analysis Set: ENR
- Table 14.1.4 Disposition by Site, Cohort B Analysis Set: ENR

#### PROTOCOL DEVIATIONS

- Table 14.1.5 Minor and Major Protocol Deviations overall and by site, Cohort A Analysis Set: SAF
- Table 14.1.5 Minor and Major Protocol Deviations overall and by site, Cohort B Analysis Set: SAF

#### DEMOGRAPHICS AND BASELINE CHARACTERISTICS

- Table 14.1.6 Demographics and Baseline Characteristics, Cohort A Analysis Set: SAF
- Table 14.1.6 Demographics and Baseline Characteristics, Cohort B Analysis Set: SAF

#### MEDICAL HISTORY AND CONCOMITANT DISEASES

- Table 14.1.7 Medical History, Cohort A Analysis Set: SAF
- Table 14.1.7 Medical History, Cohort B Analysis Set: SAF

#### PRIOR AND CONCOMITANT MEDICATIONS

- Table 14.1.8 Prior and Concomitant Medications, Cohort A Analysis Set: SAF
- Table 14.1.8 Prior and Concomitant Medications, Cohort B Analysis Set: SAF

#### EXPOSURE AND COMPLIANCE

- Table 14.1.9 Exposure and Compliance, Cohort A Analysis Set: SAF
- Table 14.1.9 Exposure and Compliance, Cohort B Analysis Set: SAF

#### EFFICACY

- Table 14.2.2.1 SBR comparison between FL and WLR, Zeiss camera Cohort A Analysis Set: FAS
- Table 14.2.2.2 SBR comparison between FL and WLR, Cohort B Analysis Set: FAS

- Table 14.2.3.1 SBR comparison between FL and WLR – Zeiss Image Analysis, Cohort A Analysis Set: FAS
- Table 14.2.3.2 SBR comparison between FL and WLR – Image Analysis, Cohort B Analysis Set: FAS

- Table 14.2.4.1 SBR comparison between B1and B2 – FL Analysis Set: FAS

- Table 14.2.4.2 SBR comparison between B1 and. B2– WLR Analysis Set: FAS

- Table 14.2.5.1 Surgeon Rating Scale, Cohort A Analysis Set: FAS

- Table 14.2.5.1 Surgeon Rating Scale, Cohort B Analysis Set: FAS

- Table 14.2.6.1 Correlation Between Surgeon Rating Scale and SBR for Zeiss device, Cohort A - Analysis Set: FAS

- Table 14.2.6.2 Correlation Between Surgeon Rating Scale and SBR, Cohort B Analysis Set: FAS

- Table 14.2.7.1 SBR and Surgeon Rating Scale for Zeiss device Cohort A, FL Analysis Set: FAS

- Table 14.2.7.2 SBR and Surgeon Rating Scale Cohort B, FL Analysis Set: FAS

- Table 14.2.8 Optimal cut-off point of SBR Cohort A and B, FL- Analysis Set: FAS

- Table 14.2.9.1 Surgeon nerve dissecting time saved, Cohort A Analysis Set: FAS

- Table 14.2.9.1 Surgeon nerve dissecting time saved, Cohort B Analysis Set: FAS

#### SAFETY

- Table 14.3.1.1 Overview of Averse events and Treatment Emergent Adverse Events in Cohort A Analysis Set: SAF

- Table 14.3.1.1 Overview of Averse events and Treatment Emergent Adverse Events in Cohort B (same table presented in separate page) Analysis Set: SAF

- Table 14.3.1.2 TEAEs incidence primary System Organ Class and Preferred Term Cohort A- Analysis set: SAF

- Table 14.3.1.2 TEAEs incidence primary System Organ Class and Preferred Term Cohort B Analysis set: SAF

- Table 14.3.1.3 Infusion Related Reactions- by Primary SOC and PT, Cohort A Analysis set: SAF

- Table 14.3.1.3 Infusion Related Reactions- by Primary SOC and PT, Cohort B Analysis set: SAF

- Table 14.3.1.4 Serious TEAEs by SOC and PT,Cohort A Analysis set: SAF

- Table 14.3.1.4 Serious TEAEs by SOC and PT, Cohort B Analysis set: SAF

- Table 14.3.1.5 Related TEAEs by MedDRA System Organ Class and Preferred Term, Cohort A Analysis set: SAF

QMS Document Name: Statistical Analysis Plan	Page 26 of 29
QMS No (include version ref): STF-015-GL.02	Document date: 09JUL2019
CONFIDENTIAL	

Table 14.3.1.5 Related TEAEs by MedDRA System Organ Class and Preferred Term, Cohort B- Analysis set: SAF  
 Table 14.3.1.6 Serious Related TEAEs by SOC and PT, Cohort A Analysis set: SAF  
 Table 14.3.1.6 Serious Related TEAEs by SOC and PT, Cohort B Analysis set: SAF  
 Table 14.3.1.7 TEAEs Leading to Study Discontinuation by SOC and PT, Cohort A Analysis set: SAF  
 Table 14.3.1.7 TEAEs Leading to Study Discontinuation by SOC and PT, Cohort B Analysis set: SAF  
 Table 14.3.1.8 Adverse Device Effects, Cohort A Analysis set: SAF  
 Table 14.3.1.8 Adverse Device Effects, Cohort B Analysis set: SAF  
 Table 14.3.1.9 TEAEs by Primary SOC and PT by intensity, Cohort A Analysis set: SAF  
 Table 14.3.1.9 TEAEs by Primary SOC and PT by intensity, Cohort B Analysis set: SAF  
 Table 14.3.1.10 Related TEAEs by Primary SOC and PT by intensity, Cohort A Analysis set: SAF  
 Table 14.3.1.10 Related TEAEs by Primary SOC and PT by intensity, Cohort B Analysis set: SAF  
 Table 14.3.1.11 TEAEs by Primary SOC and PT by Outcome, Cohort A Analysis set: SAF  
 Table 14.3.1.11 TEAEs by Primary SOC and PT by Outcome, Cohort B Analysis set: SAF  
 Table 14.3.1.12 TEAEs by PT, Cohort A Analysis set: SAF  
 Table 14.3.1.12 TEAEs by PT, Cohort B Analysis set: SAF  
 Table 14.3.1.13 Serious TEAEs by PT, Cohort A Analysis Set: SAF  
 Table 14.3.1.13 Serious TEAEs by PT, Cohort B Analysis Set: SAF  
 Table 14.3.1.14 Incidence of Related TEAEs by PT, Cohort A Analysis Set: SAF  
 Table 14.3.1.14 Incidence of Related TEAEs by PT, Cohort B Analysis Set: SAF  
 Table 14.3.1.15 Summary of Treatment-Emergent Serious adverse events and Deaths, Cohort A Analysis Set: SAF  
 Table 14.3.1.15 Summary of Treatment-Emergent Serious adverse events and Deaths, Cohort B Analysis Set: SAF  
**SAFETY: VITAL SIGNS AND OXYGEN SATURATION**  
 Table 14.3.2.1.1 Vital Signs and Oxygen Saturation, Cohort A Analysis set: SAF  
 Table 14.3.2.1.2 Vital Signs and Oxygen Saturation, Cohort B Analysis set: SAF  
 Table 14.3.2.2.1 Vital Signs and Oxygen Saturation - Categorized by Reference Ranges, Cohort A Analysis set: SAF  
 Table 14.2.2.2.2 Vital Signs and Oxygen Saturation - Categorized by Reference Ranges, Cohort B Analysis set: SAF  
**SAFETY: LABORATORY PARAMETERS**  
 Table 14.3.3.1.1 Laboratory Parameters (Quantitative), Cohort A Analysis set: SAF  
 Table 14.3.3.1.2 Laboratory Parameters (Quantitative), Cohort B Analysis set: SAF  
 Table 14.3.3.2.1 Laboratory Parameters (Quantitative) by Derived Categories, Cohort A Analysis Set: SAF  
 Table 14.3.3.2.2 Laboratory Parameters (Quantitative) by Derived Categories, Cohort B Analysis Set: SAF  
 Table 14.3.3.3.1 Laboratory Parameters (Qualitative), Cohort A Analysis Set: SAF  
 Table 14.3.3.3.2 Laboratory Parameters (Qualitative), Cohort B Analysis Set: SAF  
 Table 14.3.3.4.1 Laboratory Parameters (Quantitative) – Shift Table Regarding Reference Ranges and Clinical Significance, Cohort A Analysis Set: SAF  
 Table 14.3.3.4.2 Laboratory Parameters (Quantitative) – Shift Table Regarding Reference Ranges and Clinical Significance, Cohort B Analysis Set: SAF  
 Table 14.3.3.5.1 Laboratory Parameters (Qualitative) – Shift Table, Cohort A Analysis Set: SAF  
 Table 14.3.3.5.2 Laboratory Parameters (Qualitative) – Shift Table, Cohort B Analysis Set: SAF  
